The primary outcome for this Aim will be BOLD activation during the A1 phase of the MID task. The effects of Saracatinib treatment on activation will be assessed using linear mixed models. In these models, BOLD response will represent the dependent measure and family history status (FHP vs. FHN) will represent a between-subjects explanatory variable, while treatment (placebo vs. Saracatinib) and ROI (NAcc vs. OFC) will be included as within-subjects factors. All 2-way interactions will be modeled and interpreted using graphical displays and appropriate post-hoc tests. In the above analysis, we anticipate a family history by treatment by ROI interaction explained by significant NAcc decreases and significant OFC increases in BOLD response due to Saracatinib treatment among FHP subjects. Secondary analyses will include the above analysis performed for activation levels observed during the A2 phase and examination of additional ROIs as well as dose and. Similar models as described, excluding phase as a factor, will be used to model BART and EDT outcomes (subsidiary hypothesis). In these models, we expect a family history by treatment interaction such that each of these impulsivity measures are reduced by Saracatinib treatment among FHP individuals.

Aim 2

BOLD signal activation in the anterior cingulate cortex (ACC) observed during False Alarms of the GNG task will represent the primary outcome in this Aim. The effects of Saracatinib treatment on activation will be assessed using linear mixed models with family history (FHP vs. FHN) included as a between-subjects factor and treatment (placebo vs. Saracatinib) and response type (false alarms vs. correct rejections) as within-subjects factors. A significant family history by treatment by response type interaction explained by increased BOLD activation due to Saracatinib during false alarms in both groups, but more markedly in FHN, will be supportive of our hypothesis. We will consider other regions (BA9, BA44/45, BA47, Insula, VS) represented as additional within-subjects factors in the model described above. In this analysis, we expect Saracatinib to reduce BOLD signal activation among FHP in each of the regions during correct rejections.

Aim 3

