Linear mixed models will be used to evaluate the effects of family history on NAcc BOLD response during the ACR task. These models will include family history (FHP vs. FHN) as a between-subjects factor and type of Cue (ETOH-related vs. non-EOTH) as a within-subjects factor. We anticipate a significant group by cue interaction such that FHP subjects will respond with greater NAcc BOLD signal to alcohol-related cues vs. non-alcohol cues compared to matched FHN subjects and subsequently experience a greater reduction in NAcc BOLD response following Saracatinib administration.

Aim 4

The same statistical models described for Aim 1 will be used to evaluate the effects of Saracatinib and family history on NAcc and OFC activation during the A1 phase of the PIT-in

modified MID task. In these models, however, we will include Cue Type (PIT-related vs. Non-PIT-related) as an additional within-subjects variable. We expect a significant family history by treatment by cue type by region interaction explained by significant NAcc decreases and significant OFC increases in BOLD response due to Saracatinib treatment among FHP subjects, with these effects most exaggerated during the presentation of PIT-related cues. In addition, using regression we can test whether PIT responses (using the out-of-scanner version used in all data from study 126237) show the expected learning effect.

7. Risks and Data Monitoring Plan:

Under some circumstances, it can be a risk for genetic information about subjects to be known. Variation in some genes is known to be directly related to risk for certain illnesses. Other genes we will be studying in subject DNA may be shown at some point in the future to be related to illnesses. Since the results of these genetic tests may allow prediction of risk of illness in some cases, we will make every effort to keep the results confidential (only scientists working on this research project will know the results). We will not make any of our laboratory results available to subjects, nor will we add them to any medical record or release them to others.

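### The interaction terms stated for Aim 1, and reused for Aim 4, omit the three-way and four-way interactions that those aims predict

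*Combined protocol and SAP*

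**What the plan says.** Section 6b, Aim 1, describes a linear mixed model for BOLD response in the A1 phase of the MID task. Family history (FHP, FHN) is the between-subjects factor. Treatment (placebo, saracatinib) and ROI (NAcc, OFC) are within-subjects factors. The interaction structure is given in one sentence: "All 2-way interactions will be modeled and interpreted using graphical displays and appropriate post-hoc tests". The next sentence reads: "In the above analysis, we anticipate a family history by treatment by ROI interaction explained by significant NAcc decreases and significant OFC increases", attributed to saracatinib among FHP subjects.

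The same paragraph says that similar models serve for BART and EDT, where "we expect a family history by treatment interaction such that each of these impulsivity measures are reduced". That prediction is two-way.

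Aim 2 treats "A significant family history by treatment by response type interaction" as supporting its hypothesis and states no interaction order for its model.

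Aim 4 says: "The same statistical models described for Aim 1 will be used to evaluate the effects of Saracatinib and family history", here on NAcc and OFC activation in the modified MID task. It continues: "we will include Cue Type (PIT-related vs. Non-PIT-related) as an additional within-subjects variable". The prediction is "We expect a significant family history by treatment by cue type by region interaction", "with these effects most exaggerated during the presentation of PIT-related cues".

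No sentence in Section 6b says that a three-way or four-way term is in the Aim 1 or Aim 4 model.

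**The concern.** The Aim 1 sentence is the only one in Section 6b that states an interaction order, and it governs that aim's primary outcome. With three two-level factors, a model with all main effects and all two-way interactions lacks exactly one term, and that is the term the aim predicts. The model then forces the drug-by-ROI pattern to be equal in FHP and FHN, which is the equality the aim expects to reject. Aim 4 inherits the structure and lacks five terms, including the predicted one.

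An analyst who follows the text has no test of either prediction; one who adds the terms departs from the written plan. Sections 5.1 and 6 also say that the study is meant to estimate effect sizes and to inform the power of later studies. If the two-way model were fitted and the groups truly differed in drug-by-ROI pattern, the group-specific drug effects carried forward from it would be distorted.

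**Working it through.** The plan gives no effect size, variance or power figure for this point, so there is no figure of its own to reproduce. The check has two parts: a count of terms, and an illustration with assumed effects.

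**Term count** (factors from Section 6b, all with two levels)

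| | Aim 1 (3 factors) | Aim 4 (4 factors) |
|---|---|---|
| Cells | 2 × 2 × 2 = 8 | 2 × 2 × 2 × 2 = 16 |
| Intercept + main effects + two-way terms | 1 + 3 + 3 = 7 | 1 + 4 + 6 = 11 |
| Left out | 1 three-way | 4 three-way + 1 four-way = 5 |
| Predicted term | three-way: left out | four-way: left out |

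**Illustration, Aim 1.** Assumptions, in arbitrary units: equal groups, complete data, independent errors of equal variance. True drug effects (saracatinib minus placebo, NAcc/OFC) are -0.5/+0.5 in FHP and 0/0 in FHN.

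- Drug-by-ROI pattern, OFC effect minus NAcc effect: FHP 0.5 - (-0.5) = 1.0; FHN 0.
- Three-way contrast: 1.0 - 0 = 1.0. Spread over 8 cells, its effect-coded coefficient is 1.0/8 = 0.125.
- Leaving the term out shifts every cell mean by 0.125 in size. A drug effect is the difference of two cells with opposite signs on that term, so it shifts by 2 × 0.125 = 0.25.
- Fitted FHP: -0.5 + 0.25 = -0.25 and 0.5 - 0.25 = +0.25.
- Fitted FHN: 0 - 0.25 = -0.25 and 0 + 0.25 = +0.25.

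The FHP effects are halved and FHN acquires effects of the same size. With the three-way term added (8 parameters), the truth is returned exactly. If the pattern is the same in both groups, the three-way contrast is 0 and so is the shift.

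**How far the split depends on the assumptions** (same true effects)

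- Group sizes 35 and 45 (FHP, FHN), independent errors: the fitted common pattern is 1.0 × 35/80 = 0.4375, so the effects are about -0.219/+0.219 in both groups.
- Equal groups and equal variances, but correlated measures (0.3 between ROIs within a treatment; 0.3 between treatments in NAcc and 0.7 in OFC; 0.2 across both), fitted by generalised least squares: FHP -0.125/+0.375 and FHN -0.375/+0.125.

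In each case the pattern is forced to be equal in the two groups. How the error falls on the individual drug effects varies.

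**Illustration, Aim 4** (equal groups, independent equal-variance errors). Assumed FHP effects are -0.7/+0.7 for PIT-related cues and -0.3/+0.3 for the others, with FHN at 0.

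- Two-way terms only: the patterns 1.4, 0.6, 0 and 0 are averaged to 2.0/4 = 0.5, so the fit is -0.25/+0.25 in both groups under both cues.
- All three-way terms added (15 parameters): the four-way contrast of 1.4 - 0.6 = 0.8 is still forced to 0, and drug effects shift by 2 × 0.8/16 = 0.1. FHP is fitted as -0.6/+0.6 and -0.4/+0.4, and FHN shows false effects of 0.1 in size.
- Full model (16 parameters): the truth is returned.

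**The case against.** The strongest reply is that this is a slip of wording. The sentence says that all two-way interactions are modeled, not that only these are. The next sentence places the three-way interaction in the same analysis, and Aims 2 and 4 also treat higher-order interactions as model results. An analyst reading the whole paragraph would probably fit the full factorial. That stands as a reading of intent, and it limits the seriousness. It does not put the predicted terms into the stated model. The post-hoc tests mentioned are for interpreting the two-way interactions, so they do not supply the missing term either.

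Second, Section 6a says that signal estimates in each ROI are examined separately with Bonferroni correction, and NAcc and OFC are among its primary ROIs. In a single-ROI Aim 1 model, family history by treatment is the highest interaction, so group-specific drug effects would be estimated without this distortion. This also stands, and it narrows the harm to effect sizes. It is not a full answer: separate models do not test the ROI interaction, and that paragraph describes a symptom provocation task that appears nowhere else in the plan.

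Third, all effect sizes above are assumed. A reader might infer that the FHP effects would be halved in general, or whenever the two ROIs have equal variance. The documents specify no covariance, and the correlated example above has equal variances but a different split. A reader might also infer that the Section 4 comparison, NAcc in FHP on saracatinib against FHN on placebo, always escapes distortion. It does with equal groups and independent equal-variance errors, but with groups of 35 and 45 it is off by 0.031 in the same example. Neither general statement is supported.

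**Conclusion.** The point holds as a specification error in the written model: the interaction terms stated for Aim 1, and carried into Aim 4, omit the interactions those aims predict. A model fitted as stated has 7 of 8 parameters in Aim 1 and 11 of 16 in Aim 4, and cannot test either prediction. This follows from the text alone and needs no assumed numbers.

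The effect on estimates is conditional. It arises only if the two-way model is fitted literally and the drug-by-ROI pattern truly differs between FHP and FHN (for Aim 4, if any omitted interaction is real). The -0.25/+0.25 figure is an illustration under assumed effects, equal groups and independent equal-variance errors; the documents give no basis for a general size. The documents also do not show that the sponsor intends to leave the terms out, and a full factorial is the likelier intention.

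The BART and EDT models are unaffected if read as having no ROI factor. That reading is an inference, since the text says only that phase is excluded, but it is sensible for behavioural outcomes. Correcting the text is worthwhile because the sentence governs a primary outcome and the repair costs almost nothing.

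**What to change.** In Section 6b, Aim 1, replace the sentence on interactions with: *All main effects, all two-way interactions and the family history × treatment × ROI interaction will be modeled; the three-way term is the test of the stated prediction.* Follow it with the plan's own contrasts: saracatinib versus placebo within each ROI among FHP.

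In Aim 4, state that all interactions up to family history × treatment × cue type × region are included, and that the four-way term tests the prediction.

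The BART and EDT models can keep the two-way structure; a few words confirming that they have no ROI factor would remove doubt.

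The cost is two sentences, adding one model term in Aim 1 and five in Aim 4 (four three-way and one four-way). No new data, participants or procedures are needed.

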The current study consists of ~7-8 hours of screening on one day, and 2 subsequent, separate 6 ½-7 hour study days, each separated by ~ 1 week. It proposes to examine 90 subjects (45 FHP, 45 FHN), using the experimental Fyn-Src family protein tyrosine kinase inhibitor drug Saracatinib, (AZD0530), which blocks the glutamate system more specifically and predictably than memantine. AZD0530 was developed by Astra Zeneca as an anti-cancer drug in which is currently in clinical trials. The relevant Investigator's Brochure is appended. [name] is obtaining permission from Astra Zeneca to use this new drug in the context we describe by being added to Astra Zeneca's existing approved IND. We will use one dose of the new drug, (125 mg versus placebo in random assignment single-blind fashion), administered 90 minutes prior to the MRI and other measures, in three separate experimental study visits. We will compare family history positive for alcoholism (FHP; i.e., affected parent plus other close relatives) to matched family history negative (FHN; i.e., no affected first-degree relative). This project explores the

effects of 125 mg of Saracatinib vs placebo in a single-blind, randomized, counterbalanced manner on alcoholism risk-relevant tasks.

4. MAJOR HYPOTHESES:

1. AZ0D530 trial with functional MRI Monetary Incentive Delay (MID) Task.

During the A1 (reward prospect) phase of the fMRI MID task, via Saracatinib blockade of NMDA receptors, compared to placebo, dopaminergic imbalance in reward circuitry of FHP will be “reset” such that excessive nucleus accumbens (NAcc) activation during the A1 phase will be normalized and more closely resemble that of matched FHN individuals on placebo.

Importance: tests hypothesis of DA/NMDA imbalance in reward circuitry as a risk factor for alcoholism and sheds light on potential therapeutic interventions. Logical extension of suggestive preliminary data gathered in prior phase of CTNA with memantine.

2. AZ0D530 trial with functional MRI Go/No-Go (GNG) Task.

The GNG task measures the ability to inhibit response to a pre-potent stimulus, assessing an orthogonal aspect of behavioral impulsivity to the MID task, but one also hypothesized to be related to alcoholism risk.

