Statistical Parametric Mapping (SPM5) analyses will test pre- to post-treatment differences in fMRI regions of interest (ROIs) during decision making for owned and control items on the symptom provocation task. The primary ROIs for treatment effects include bilateral NAcc, ACC and bilateral OFC. These and other task-relevant ROIs will be defined as 16 mm diameter spheres around x, y, z coordinates determined from our current data. Mean estimates of signal change (i.e., beta-weights from fMRI regression models) within each ROI will be examined separately using Bonferroni correction will be used to guard against alpha inflation due to multiple comparisons. As a secondary analysis, in the event that our new dataset shows somewhat different main effects of task (i.e., peak activation foci in slightly different regions), we can use the Wake Forest University toolbox to draw anatomically-based regions-of-interest. SPM analyses can then test these using averaged % BOLD signal change estimates from the entire region, or SPM small-volume correction to determine the peak group effect difference within the study ROIs.

Mapping Abnormal Responses Across fMRI tasks onto Functional Brain Systems

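### Hypothesis 1 concerns NAcc alone, but the only effect named for Aim 1 is a NAcc-versus-OFC three-way interaction; the NAcc contrasts that would test the hypothesis are not prespecified

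*Combined protocol and SAP*

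**What the plan says.** Section 4, Hypothesis 1, predicts that in FHP subjects given saracatinib "excessive nucleus accumbens (NAcc) activation during the A1 phase will be normalized and more closely resemble that of matched FHN individuals on placebo". The claim names one region and one benchmark.

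Section 6b, Aim 1, sets the outcome without naming a region: "The primary outcome for this Aim will be BOLD activation during the A1 phase of the MID task". The mixed model has family history as the between-subjects factor, and "treatment (placebo vs. Saracatinib) and ROI (NAcc vs. OFC) will be included as within-subjects factors". On interactions it says: "All 2-way interactions will be modeled and interpreted using graphical displays and appropriate post-hoc tests". It then states its expectation: "we anticipate a family history by treatment by ROI interaction explained by significant NAcc decreases and significant OFC increases in BOLD response", attributed to saracatinib in FHP subjects.

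Section 6a also touches on regions: "The primary ROIs for treatment effects include bilateral NAcc, ACC and bilateral OFC", each to be examined separately with a Bonferroni correction. The sentence that introduces this describes pre- to post-treatment differences "during decision making for owned and control items on the symptom provocation task", which is not a task in this study.

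Aim 3 models NAcc alone. Aim 4 reuses the Aim 1 models and adds cue type.

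**The concern.** The hypothesis and the analysis ask different questions. Hypothesis 1 needs three facts about NAcc: FHP exceed FHN on placebo, saracatinib lowers the FHP value, and the lowered value lies closer to FHN on placebo. The three-way interaction supplies none of them. It compares the two groups on how far the drug response in NAcc differs from the drug response in OFC.

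A true NAcc effect can therefore be missed when OFC shifts the same way, and a significant interaction can arise with NAcc unchanged. The plan is also unclear on whether the three-way term is in the model at all, since only two-way terms are listed. The study is meant to deliver effect sizes for later trials, and a NAcc-minus-OFC difference is the wrong estimate to carry forward for a NAcc hypothesis.

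**Working it through.** **Inputs from the documents.** Section 3 gives the size: "It proposes to examine 90 subjects (45 FHP, 45 FHN"). Each subject receives both drug and placebo. The factors are those of section 6b, Aim 1.

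**Inputs not in the documents, assumed here.** Two-sided alpha 0.05; SD of the drug-minus-placebo change equal to 1 in each ROI; a family history by treatment effect on NAcc of *d* = 0.6 SD, with other values shown; correlation ρ between the NAcc and OFC changes from 0 to 0.7; complete data. The plan states no power, SD or effect size and does not derive 45 per group, so it has no figure to reproduce.

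**What each test compares.** Let D be a subject's saracatinib-minus-placebo change.

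- NAcc-only family history by treatment: D(NAcc), FHP against FHN. Standardised effect = *d*.
- Three-way: D(NAcc) − D(OFC), FHP against FHN. The SD is √(2(1−ρ)). If OFC moves *k* times as far as NAcc, the standardised effect is *d*(1−*k*)/√(2(1−ρ)).

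Two results need no assumed values. At *k* = 1 the three-way effect is zero. If NAcc is unchanged and OFC shifts by *d*, its size is *d*/√(2(1−ρ)), the same as when NAcc shifts and OFC does not.

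**Power.** Noncentral t with 88 df and noncentrality = effect × √(45/2) = effect × 4.743.

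The NAcc-only test has 47% at *d* = 0.4, 80% at 0.6 and 96% at 0.8, whatever OFC does.

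Three-way test at *d* = 0.6:

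| OFC change relative to NAcc | ρ = 0 | ρ = 0.3 | ρ = 0.5 | ρ = 0.7 |
|---|---|---|---|---|
| None (*k* = 0) | 51% | 66% | 80% | 95% |
| Half, same direction (*k* = 0.5) | 17% | 22% | 29% | 44% |
| Equal, same direction (*k* = 1) | 5% | 5% | 5% | 5% |
| Equal and opposite, as predicted (*k* = −1) | 98% | over 99% | over 99% | over 99% |

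Example: *k* = 0, ρ = 0 gives 0.6/√2 = 0.424, noncentrality 2.01, power 51%. With *k* = 0, the two tests are equal at ρ = 0.5, where √(2(1−ρ)) = 1; above that the three-way test is stronger.

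By symmetry, an OFC-only shift of 0.6 SD makes the three-way test significant 51%, 66%, 80% and 95% of the time across these correlations, while the NAcc-only test stays at 5%. A simulation with 20,000 replicates agreed for the none, equal, opposite and OFC-only cases.

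**Is the NAcc family history by treatment interaction enough by itself?** No. Suppose FHP exceed FHN on placebo by *e* and the drug lowers NAcc by *e* in both groups. FHP on drug then equal FHN on placebo, so the hypothesis holds exactly, yet the interaction is −*e* − (−*e*) = 0. Hypothesis 1 makes no use of FHN on drug, so its test has to rest on the cell contrasts.

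**The case against.** A reader might infer that the plan would claim success on an OFC change alone. The documents do not support that. The Aim 1 wording is an expectation, not a decision rule, and it ties the interaction to NAcc falls together with OFC rises; an OFC-only result would not match it. The plan names a primary outcome for Aim 1, not a primary test.

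A reader might also infer that NAcc is never tested. That too goes beyond the text. Follow-up tests are promised, and section 6a lists NAcc among ROIs to be examined separately. What stands is that the follow-up tests are unspecified and attached to two-way terms, no rule covers NAcc when the interaction is null, and the section 6a passage is written around a task this study does not use. It also gives no FHN-placebo benchmark.

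Third, the three-way test is not weaker in general. It does better under the predicted opposite pattern, or when OFC is unchanged and the correlation exceeds 0.5. The dissociation looks deliberate: Aim 4 repeats it, and the MID task description links OFC to abstract reward. This is a good reason to keep the test, but a rise in OFC is an extra prediction, not Hypothesis 1.

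Finally, this is a pilot meant to assess effect sizes (section 5.1) and inform power for later studies (section 6), and every NAcc contrast can be estimated from the planned data. That lowers the stakes without removing the mismatch.

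**Conclusion.** The point holds as a gap in prespecification. The one effect named for Aim 1 does not test Hypothesis 1, the contrasts that would test it are not named, and the text does not clearly place the three-way term in the model.

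The direction of the problem follows from algebra: the interaction cancels when NAcc and OFC move together and responds to OFC alone. Its size depends on the assumed effect, SDs, alpha and correlation. Against 80% for the NAcc-only test at 0.6 SD, three-way power runs from 5% when both regions move equally to about 98% or more under the predicted pattern. The 80% reflects the chosen effect, not a property of this trial. The change is a cheap improvement; the documents do not show that the design fails.

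**What to change.** In section 6b, Aim 1:

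1. State that the mixed model includes the family history by treatment by ROI term.
2. Prespecify three NAcc A1-phase contrasts from that model as the test of Hypothesis 1, reported with estimates and 95% confidence intervals whether or not the three-way term is significant: (a) FHP v FHN on placebo, to show whether there is an excess; (b) saracatinib minus placebo within FHP; (c) FHP on saracatinib v FHN on placebo, shown beside (a). State that a non-significant (c) is not proof of normalization.
3. Report the NAcc family history by treatment interaction to show whether any effect is specific to FHP.
4. Keep the NAcc/OFC three-way interaction as a secondary test of dissociation.
5. State how the multiplicity correction covers these contrasts, and replace the section 6a text on the symptom provocation task with text for this study's tasks.

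Aim 4 reuses the Aim 1 models, so the same clarification is needed there.

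The cost is SAP wording, with the same scans, data and software. The predicted dissociation is no longer the lead test, and there are more planned contrasts to correct for. For a 45 v 45 comparison, the difference detectable with 80% power is (1.960 + 0.842) × √(2/45) = 0.59 SD at two-sided 0.05, and (2.394 + 0.842) × √(2/45) = 0.68 SD at 0.05/3 (normal approximation).

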AZOD530's blockade will act to “reset” dopaminergic imbalance in extended reward system circuitry of FHP so that abnormal NAcc, ACC, and DLPFC activation during response inhibition will be normalized and more closely resemble that of matched FHN individuals in the placebo condition.

Importance: tests hypothesis of DA/NMDA imbalance in response inhibition circuitry as a risk factor for alcoholism. Logical extension of data gathered in prior phase of CTNA.

Extended network analysis using functional connectivity approaches will show interrelationships among neural circuits responsible for response inhibition (GNG) and motivation (MID) and additionally their alteration by Saracatinib in FHP (exploratory).

3. AZ0D530 trial with fMRI Alcohol Cue Reactivity (ACR) task (AKA ‘NAC’ task). The ACR task in alcohol users is related to the brain's response in reward-related regions to wanting and craving of alcohol versus matched soft drink stimuli. Prior data also suggest that Saracatinib will suppress cue-induced alcohol craving, perhaps more markedly in FHP. **Aim:** to examine NAcc response to alcohol-related versus control images using an existing ACR task.

Major hypothesis. FHP who use alcohol will respond with greater NAcc BOLD signal to alcohol-related cues vs. non-alcohol cues than matched FHN who use alcohol. **Subsidiary hypothesis.** Alcohol-using subjects in general will show a reduced response to alcohol images in the ACR task during the Saracatinib condition, but more markedly in FHP.

Importance: examines additional forms of responsiveness likely relevant to initiation into alcohol misuse.

4. Pilot Task: Pavlovian-to-Instrumental Transfer (PIT) Elaboration of MIDT

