subjects in our lab^{113,114}. The GNG fMRI literature reveals that the same regions are consistently implicated. No-Go responses include anterior cingulate cortex (ACC)^{16,56,61,65,66,85,89,116}; orbitofrontal cortex (OFC)^{38,61,74,89}; dorsolateral prefrontal cortex (DLPFC)^{4,7,16,21,38,48,65,66,74,89,122}; inferior parietal lobule (IPL)^{4,7,16,38,89,61,122}; and pre-motor area BA6 and caudate^{89,93,122}. ACC seems essential for conflict response, decision formation/action selection, and error monitoring^{15,65,129-131} and ventrolateral prefrontal cortex plays a role in response inhibition¹³¹. Children activate these regions and amygdala more than adults¹⁴, suggesting a less efficient response inhibition system. Impulsive normal subjects activate paralimbic areas and OFC more during response inhibition⁶¹ likely to maintain behavioral inhibition. Substance abusers may show less task-related ACC and PFC activity^{35,64}.

fMRI Alcohol Cue Reactivity (ACR) Task:

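### Aim 2's supportive pattern, a false-alarm ACC rise that is larger in FHN, does not show the normalization of FHP that Hypothesis 2 predicts

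*Combined protocol and SAP*

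**What the plan says.** Section 4, Hypothesis 2 (Go/No-Go), makes this prediction: "abnormal NAcc, ACC, and DLPFC activation during response inhibition will be normalized and more closely resemble that of matched FHN individuals". The comparator is FHN on placebo. The hypothesis does not say whether abnormal means too high or too low. Hypothesis 1 does give a direction: "excessive nucleus accumbens (NAcc) activation during the A1 phase will be normalized and more closely resemble that of matched FHN individuals on placebo".

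Section 6b, Aim 2, states that ACC signal "observed during False Alarms of the GNG task will represent the primary outcome in this Aim". The linear mixed model has family history between subjects, and treatment and response type (false alarms, correct rejections) within subjects. Support is described as a significant three-way interaction of this form: "increased BOLD activation due to Saracatinib during false alarms in both groups, but more markedly in FHN, will be supportive of our hypothesis".

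For further regions (BA9, BA44/45, BA47, insula, VS), Aim 2 adds that "we expect Saracatinib to reduce BOLD signal activation among FHP in each of the regions during correct rejections".

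The other aims put the effect, or the larger effect, in FHP. Aim 1, whose models Aim 4 reuses, expects "significant NAcc decreases and significant OFC increases in BOLD response due to Saracatinib treatment among FHP subjects". Aim 3 expects FHP to "subsequently experience a greater reduction in NAcc BOLD response following Saracatinib administration".

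**The concern.** The hypothesis concerns where FHP ends up relative to FHN on placebo. The supportive pattern concerns which group responds more to the drug. These are different quantities, and the second does not determine the first. As written, Aim 2's primary result could be reported as supporting Hypothesis 2 without showing that FHP was abnormal on placebo or that FHP moved toward FHN.

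Sections 5.1 and 6 present the study as a source of effect sizes for planning larger studies. An effect labelled as normalization that does not measure it would be a poor basis for that, although the plan does not say that this particular interaction will be carried forward.

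**Working it through.** The plan gives no figure to reproduce. All effect values and correlations below are assumptions, in SDs of a single-session ACC estimate. Only the group size (45 per group, section 5.2) and the model factors (Aim 2) come from the documents.

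**Definitions, ACC.** On false alarms, g = FHP minus FHN on placebo, x = drug change in FHP, y = drug change in FHN. On correct rejections the drug changes are xC and yC.

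- Hypothesis 2 (normalization): |g + x| < |g|.
- Aim 2 pattern: y > x > 0, with interaction I = (x - y) - (xC - yC) different from zero.

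Neither part of the Aim 2 pattern contains g. Normalization does not contain y.

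**By the sign of g, when x > 0.**

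- g = 0 or g > 0: |g + x| > |g|, so FHP moves away from FHN on placebo.
- g < 0: FHP moves closer only if x < 2|g|. The size of y is irrelevant.

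**Example: x = 0.2, y = 0.5, xC = yC = 0.** I = 0.2 - 0.5 = -0.3 in every row.

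| g | g + x | FHP relative to FHN on placebo |
|---|---|---|
| -0.4 | -0.2 | closer |
| 0 | +0.2 | further |
| +0.4 | +0.6 | further |

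**FHP-only reset.** With g = -0.4, x = 0.4, y = 0 and xC = yC = 0, g + x = 0, which is complete normalization. I = +0.4, the opposite sign.

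**Dependence on correct rejections.** With x = 0.2 and y = 0.5 but xC = -0.3 and yC = 0, I = -0.3 - (-0.3) = 0, and the interaction part of the pattern fails. The values of I above therefore depend on the zero correct-rejection changes. The absence of g from the pattern does not.

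**Changing FHN to FHP.** With x = 0.6, y = 0.3 and g = +0.5, the gap goes from 0.5 to 1.1. Swapping the letter does not cure the problem.

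**Precision of the contrasts that would show normalization.** Assume complete data, equal variances and a within-subject correlation r of 0.3 to 0.8. The 95% half-widths are:

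- Either gap to FHN on placebo: t(0.975, 88) × sqrt(2/45) = 0.419.
- FHP drug change: t(0.975, 44)/sqrt(45) × sqrt(2(1 - r)) = 0.355 (r = 0.3) to 0.190 (r = 0.8).
- Family history by treatment: 0.419 × sqrt(2(1 - r)) = 0.496 to 0.265.

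The three-way term also needs correlations between trial types, which the documents do not give, so I quote no half-width for it.

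**Why the direction must be fixed beforehand.** The observed g and x share the FHP placebo mean. With no true gap and no drug effect, their correlation is -sqrt(1 - r)/2, that is -0.418 to -0.224. They then have opposite signs with probability 0.5 + arcsin(sqrt(1 - r)/2)/π = 0.637 to 0.572, not 0.5. Opposite signs, the first sign of a reset, are thus favoured by chance.

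**The case against.** **FHP may be underactive, so a rise would be a reset.** This is possible. The Go/No-Go background reports lower ACC and PFC activity on such tasks, but in substance abusers, who are not the FHP group. It hints at g < 0 without settling it. Even then, the larger FHN rise is no evidence of normalization.

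**The hypothesis meant in Aim 2 may be the broader one.** Hypothesis 2's statement of importance speaks of DA/NMDA imbalance as a risk factor, and a weaker drug response in FHP could be read as a sign of that. If so, the plan should say it. The prediction in Hypothesis 2 is still normalization.

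**The correct-rejection prediction covers the hypothesis.** It is closer to it, being specific to FHP. But it belongs to the analysis of additional regions, is not the stated support pattern, and also lacks the FHN-placebo comparator.

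**Aim 1 names no FHN-placebo contrast either.** True. There, however, the direction is stated and the expected NAcc decrease in FHP fits it. Aim 2 has neither feature for its primary outcome.

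**Stronger readings that the documents do not support.** A reader might infer that the Aim 2 pattern contradicts Hypothesis 2. It does not, because both can hold when g < 0 and x < 2|g|. A reader might infer that any other pattern would be rejected, but Aim 2 names one supportive pattern and excludes none. A reader might take FHN as a certain misprint. The other aims make a slip plausible, but nothing confirms it. Finally, choosing false-alarm ACC is not itself a fault, since the plan notes that "ACC seems essential for conflict response, decision formation/action selection, and error monitoring".

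**Conclusion.** The point holds as a mismatch between a hypothesis and its stated support pattern, and it should be fixed. That the pattern omits the placebo gap follows from the wording alone and needs no assumed value. The illustrative sizes rest on assumed effects and, for the interaction, on the correct-rejection changes chosen. The true sign of the FHP gap is unknown from the documents, so one cannot say that Aim 2 would mislead, only that it could. No data are lost, because the planned model contains every cell needed.

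Precision is limited. Under the assumptions above, an observed placebo gap of 0.4 SD would have an interval of about ±0.42 that includes zero, so evidence that FHP is abnormal may itself be weak and should be shown.

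**What to change.** 1. Reconcile section 4 (Hypothesis 2) with section 6b (Aim 2). Correct FHN if it is a slip, or restate Hypothesis 2 if the FHN prediction is intended. Changing the letter alone is not enough.
2. State beforehand the expected direction of the FHP-minus-FHN placebo difference in ACC, for false alarms and for correct rejections.
3. Count the result as support for normalization only if (a) the placebo difference is in the stated direction, with its confidence interval reported and judged, and (b) the FHP drug change is in the opposite direction and brings FHP on saracatinib closer to FHN on placebo.
4. From the planned model, report FHP-placebo minus FHN-placebo, FHP-saracatinib minus FHN-placebo, and the FHP drug change, each with a confidence interval, for both trial types.
5. Keep the interactions as evidence of FHP specificity, not as evidence of normalization. False-alarm ACC can stay primary if justified as error monitoring.

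The cost is wording: same scans, same model. The downsides are that the stated prediction changes, some results may be less favourable to the hypothesis, and the between-group gap is less precise than the within-subject FHP change (half-width 0.42 against 0.36 to 0.19 under the assumptions above).
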